HFU-60

Hip Fracture in Individuals under 60 Years of Age. A Prospective Multi-Center Study of the Epidemiology, Treatment, Outcome and Patient Satisfaction Regarding Hip Fractures.

Study protocol

10 November 2018

HFU-60

Hip fracture in individuals under 60 years of age. A prospective multi-center study of the epidemiology, treatment, outcome and patient satisfaction regarding hip fractures.

Background:

Hip fractures are rare in young and middle aged adults, but an increase in incidence is seen in women around 50 years (Borgstrom et al. 2006, Karantana et al. 2011). Elderly hip fracture patients constitute a quite homogenic group; frail, biologically aged individuals who sustain the fracture due to a low-energy trauma, and have a high risk of mortality. The group under 60 years is more heterogenic (Zetterberg et al. 1982). Some may have severe diseases, functional limitations or alcohol/drug abuse. Others appear healthy and sustain their fracture in high-energy accidents. Some studies identify risk factors for hip fractures in younger age groups; hormonal deficiency, low cognitive function, smoking and alcohol abuse (Jackson et al. 1992, Karantana et al. 2011). Still, the literature is scarce, probably mainly because of the low incidence and the variations in both patient characteristics and injury mechanisms.

Hip fractures can be divided into intracapsular and extracapsular fractures, the latter are treated with internal fixation in all patients. For intracapsular fractures, the patient's age determines the type of surgery. In "elderly", arthroplasty is the treatment of choice in displaced fractures, this can be either a total hip arthroplasty or a hemiarthroplasty. "Younger" patients are treated with internal fixation after fracture reduction. There is no consensus regarding which age limit should be used, and the assessment is complicated by the fact that "biological age" is more relevant than chronological age. In practical use, 60, 65 or 70 years are mostly used as the divide. Arthroplasty leads to fewer reoperations, and better pain relief and function (at least during the first years). Due to an assumed long life expectancy, internal fixation is used in younger individuals, as arthroplasty might lead to complications after 10-20 years. The short term risk of complications after internal fixation – 20-50% - is usually accepted, as these patients can tolerate secondary surgery with arthroplasty after failed fixation. The exact failure rate in younger patients is not known, and they may have better ability to heal their fracture than the geriatric population. Younger patients *may* have better bone quality, better blood supply to the femoral neck and head and better nutritional status, which all promotes fracture healing. On the other hand, we suspect hip fracture to be a sign of frailty, regardless of the patient's age.

Overall Aim:

The overall aim is to investigate the epidemiology of hip fractures in younger patients (regarding hormonal status, bone density and health profiles in comparison to a standard population), analyze of trauma and fracture type, fracture treatment and outcome as well as patient satisfaction during two years.

Material and Method:

The study is a prospective multi-center cohort study of young and middle-aged adults who have incurred a hip fracture; describing epidemiology of hip fracture in this age group, clinical results and

HFU-60

patient reported outcome during two years following the hip fracture. Patients aged 18 to 59 years, who sustain an acute non-pathological hip fracture (defined by ICD-codes S72.00, S72.10 and S72.20) and are treated within four weeks at any of the participating hospitals, are invited to participate in the study. All patients are invited, regardless of medical, cognitive and functional pre-fracture status. The patients' informed consent is to be obtained before inclusion in the study.

Participating hospitals and approximate annual number of hip fractures in patients under 60 years:

- Skåne University Hospital (Malmö and Lund, Sweden) - 45
- Hvidovre Hospital (Copenhagen, Denmark) - 50
- Odense University Hospital (Odense and Svendborg, Denmark) - 50
- Kolding Hospital – part of Lillebælt Hospital (Kolding, Denmark) - 50

The projected number of included patients in the study is 200 to 300 individuals, which would require inclusion during one and a half to two years at all units, depending on the degree of patients accepting inclusion in the study. The study is mainly descriptive, wherefore power calculations are not considered feasible.

Patients are treated according to the department's standard rationale. In addition, the study will comprise interview and written enquires, blood tests regarding medical, hormonal and nutritional status, bone density measurement (DEXA scans), magnetic resonance imaging (MRI) and follow-up visits with x-ray and functional assessment. The x-ray controls are standardized to follow the standard guidelines of Hvidovre Hospital and Skåne University Hospital, which at most means three more x-rays for some patients (in total approximately 1mSv with minimal life time risk of cancer). In patients accepting study participation, the researchers are allowed to read hospital files regarding pre- and postoperative health status. Patients will be followed for two years after inclusion. Analysis of hormonal status, health profile and bone density are compared to a standard population. Risk factor analysis will be performed, regarding the risk of sustaining a hip fracture per se as well as the risk of complications and re-operations after hip fracture treatment.

As a collaborating but separate study with a separate study protocol, bone biopsies taken intra-operatively at participating Danish departments will be analyzed regarding the micro- and ultra architecture of trabecular and cortical bone by means of nano-CT and micro-CT imaging techniques.

Study inclusion and informed consent

The patient will, during admission, be invited to participate in the study by a medical doctor, nurse or physiotherapist associated to the study who will provide information regarding the study orally and in written form. The patients are usually bedridden so the interview is planned at the ward in a private room or by closed curtains. The patient can choose to have a relative or other person of choice present if so wanted. Informed consent to participate in study 5 shall be obtained prior to surgery. For study 1 to 4, informed consent given post-operatively will be accepted for inclusion if not already obtained prior to surgery together with consent to participate in study 5. The patient will at most have 24 hours to review the information to be included in study 5, but at least one hour of reflection will be given for study 1 to 5.

Follow-up scheme

	Pre-operatively	Surgery	Day 1-10	6 weeks	4 months	1 year	2 years
	Hospital			Letter or phone call****	Visit	Visit	Visit
Study inclusion	(X)		X				
Blood tests	X*		X*				
Surgery		X					
Bone biopsy**		X					
Visit					X	X	X
PROM			X (prefracture recall)	X	X	X	X
Questionnaire/ interview			X		X	X	X
Functional tests			X		X	X	
X-ray	X		X		X	X	X
MRI (MARS), if cervical fracture***			X		X	X	
DEXA scan			X*****				X

* Standard screening blood test shall be taken as early as possible, as they may be disturbed by trauma and surgery.

** Bone biopsy taken at Danish departments.

*** MRI MARS performed at Skåne University Hospital initially.

**** Phone call to patients not responding to letter.

***** DEXA no. 1 should be performed within the first month after trauma

Functional assessment is to be done on the day before discharge from the ward or the 10th day postoperatively, which day shall be noted in the protocol. Functional assessment is performed in-ward, at follow-ups at 4 months and 1 year post-operatively, not at the 2-year follow-up.

MRI with metal artefact reduction technique (MRI MARS) is performed in patients with a femoral neck fracture, dislocated and non-dislocated treated with internal fixation, to assess signs of femoral head necrosis. MRI MARS is performed early postoperatively and at follow up visits at 4 and 12 months postoperatively. In Malmö, MRI MARS is performed using Siemens commercially available standard sequences (MARS + VAT) for metal reduction imaging together with intravenous gadolinium contrast.

Patients not meeting for follow-ups will be called upon three times, thereafter they are contacted by phone, to complete the interview normally performed at the visit.

Assessment of radiographs will be performed using standardized definitions, by one of the local researchers from each of the departments and [name] will co-assess all radiographs.

Recorded data

Basic demographic indicators:

HFU-60

Gender

Age

Type of living (alone, together with someone else, institution, lacks permanent residence)

Extent of work (full time, part time, sick leave, disability pension, not working for other reason)

Health indicators:

BMI

Comorbidity (ASA and Charlson)

History of previous fractures – patient recall and medical files

Hospital admission during the year preceding the hip fracture

Use of particular medication during 5 years leading up to the fracture

Use of tobacco, alcohol or other recreational drugs – prefracture –AUDIT- and DUDIT-questionnaire.

Physical activity level

Bone mass density – DEXA scan

Regular menstruation

Laboratory blood tests:

Test:

- hemoglobin, leucocytes w. differential count, platelet count, erythrocyte sedimentation rate and/or C-reactive protein (a.s.a.p. after trauma)
- electrolytes (Na⁺, K⁺), creatinine
- total calcium + albumin, parathyroid hormone (a.s.a.p. after trauma)
- 25-hydroxyvitamin D
- alkaline phosphatase, INR
- TSH, T3, T4
- testosterone (men) / estradiol (women)
- tissue transglutaminase antibody

Purpose:

- normal blood samples and pathological
- renal function
- hypo-/hyperparathyroidism
- vitamin D deficiency
- bone metabolism, liver disease
- thyroid disease
- hypogonadism
- coeliac disease

Regarding the injury:

Information about the accident – mechanism of injury, other injuries apart from hip fracture.

Fracture type classification according to Garden (displaced vs. undisplaced) and AO – classified by local researcher, not surgeon.

Type of surgery and implant.

Outcome:

Patient reported outcome measure (PROM):

- EQ5D (3 level), EQ-VAS, Oxford hip score – prefracture recall, 6 wks, 4, 12 and 24 months.
- VAS-psr (pain, satisfaction, rehabilitation) – 6 wks, 4, 12 and 24 months.
- New mobility score (NMS) – prefracture recall, 4, 12 and 24 months.

Functional outcome – Timed up and go (TUG), 10 meter walking test (10MWT) and hand grip strength test (HGS) – in-ward, 4 and 12 months.

Clinical outcome, complications and reoperations.

Radiological outcome - definition of radiological outcome and complications in separate appendix.

HFU-60

Avascular necrosis is assessed clinically and radiologically by MRI and X-ray and findings are graded according to predefined definitions, sorting patients into one of three categories: no AVN, possible AVN, manifest AVN.

Ethical considerations

The study has been approved by ethical committees in Sweden (Regionala etikprövningsnämnden Lund (Diarienummer: 2015/28)) and Denmark (Videnskabsetisk Komité for Region Syddanmark (Projekt ID: s-20150137)), as well as permission granted to create a computer database on the subjects in accordance with the Swedish Personal Data Act (Samråd KVB, Region Skåne (Ärendenr 202-14) and the Danish Data Protection Agency (Datatilsynet for Syddanmark (Journal nr. 15/51398)). Study subjects will be included in the study only after giving their informed consent to participate in the study. The study will be conducted in accordance with the Helsinki Declaration (World Medical 2013).

Data

The Danish Data Protection Agency (Datatilsynet) has been notified regarding this project and the Danish law about personal data will be met, as well as the Swedish Personal Data Act. The following data can be acquired from the patients' medical records:

- Type of living
- Work level
- BMI
- Co-morbidity – ASA and Charlson
- History of previous fractures – patient recall and medical files
- Hospital admission during the year preceding the hip fracture
- Use of particular medication – prefracture – patient recall and medical files
- Information about the accident – mechanism of injury, other injuries apart from hip fracture.
- Fracture type classification
- Type of surgery and implant
- Radiological outcome
- Complications
- All blood test results
- MR results
- DEXA results

This information as well as the information from patient interview will give a better understanding of the patients' health status.

Budget, strategy, financial support

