## **1.a. Bone quality, demographics and hormonal status in hip fracture patients under 60 years of age.**

*First author:* [name]

*Co-authors:* (in random order) [name]; [name], [name], [name]; [name], [name]; [name].

*Last author:* [name]

*Study design:* Prospective multi-center cohort study

*Participants:* Approx. 200 individuals aged 18-60 years

*Exposure:* Acute, non-pathological hip fracture (intra- and extracapsular), regardless of trauma level

*Control group:* Cohorts of middle-aged, non-fractured individuals with DXA measurements at Odense and Skåne University Hospital

*Aim:*

1. Comparison of bone mineral density at the time of hip fracture (DXA scan) and basic risk factors for osteoporosis (BMI, smoking, etc. = variables accessible in the control groups)

Statistical analysis of categorical data using Chi-square test.

2. Descriptive analysis of other relevant factors in a young hip fracture cohort

Statistical analysis of categorical data using Chi-square test.

*Collected variables in the prospective study:*

Gender, age, BMI

Comorbidity, medication

Diet

Abuse – alcohol, drugs, tobacco, anabolic steroids

Socioeconomics (working capacity, type of living)

Fracture history (own and first-hand relatives)

Laboratory tests including hormonal status

DXA scan at the time of the fracture

Fracture pattern, type of trauma

Physical / functional level prefracture (New mobility score and others)

Health-related quality-of-life prefracture

*Hypotheses:*

There are differences in BMD and risk factors when comparing the hip fracture group with a standard control group.

Within the hip fracture group; different levels of BMD are associated with comorbidities, hormonal status and life style factors.

*Perspective/clinical relevance:*

To identify those patients who have an underlying cause or reason for sustaining a hip fracture in relatively young age and, when appropriate, initiate preventive measures for future fractures.

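### Blood samples may be drawn before surgery or on day 1-10, and the protocol warns that trauma and surgery may disturb them, but SAP 1.a tests hormonal status against BMD without using sample timing

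*Protocol*

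**What the plan says.** **Sampling.** The table under Follow-up scheme in the protocol marks blood tests in both the pre-operative and the day 1-10 columns. It does not say whether this means either occasion or both. The footnote reads "Standard screening blood test shall be taken as early as possible, as they may be disturbed by trauma and surgery". It sets no latest time.

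**How late samples arise.** Under Study inclusion and informed consent: "For study 1 to 4, informed consent given post-operatively will be accepted for inclusion if not already obtained prior to surgery". Under Material and Method, eligible patients "are treated within four weeks at any of the participating hospitals", so a pre-operative sample is not necessarily an early one.

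**Laboratory list.** The blood count/inflammation line and the calcium/albumin/PTH line each repeat the request for early sampling. The lines for thyroid tests, sex hormones and 25-hydroxyvitamin D do not.

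**Use of the results.** Material and Method states: "Analysis of hormonal status, health profile and bone density are compared to a standard population". SAP 1.a has the hypothesis "Within the hip fracture group; different levels of BMD are associated with comorbidities, hormonal status and life style factors". The only test that SAP 1.a names is the chi-square test. Its variable list includes laboratory tests but no sampling day and no pre-/post-surgery flag. For functional assessment, by contrast, the protocol asks that the day be noted.

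**The concern.** The protocol identifies a measurement problem and answers it only with an instruction to sample early. That instruction reduces the number of disturbed samples, but it does not tell the analyst what to do with those that remain. Because post-operative consent is an accepted route into studies 1 to 4, post-operative sampling is to be expected and is not a rare deviation.

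Three results are exposed:

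- the described frequency of hormonal deficiency in the cohort;
- the protocol's comparison of hormonal status with a standard population;
- the within-cohort hormone-BMD hypothesis of SAP 1.a.

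SAP 1.a aims to find patients with an underlying cause and to start prevention where appropriate, so a transient value read as a lasting deficiency bears directly on its purpose. SAP 1.b lists the same laboratory values among its adjustment variables and inherits the problem.

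**Working it through.** The plan gives no power, error-rate or effect-size figure on this point, so there is nothing to reproduce. The sample size of about 200 comes from SAP 1.a. Every shift, late share and prevalence below is an assumption, and *late* means a sample disturbed by trauma or surgery.

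**1. Apparent deficiency.** Let p be the true share below the cut-off, s the shift towards deficiency in SD units, and f the share of late samples. Then

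apparent share = (1 − f)·p + f·Φ(Φ⁻¹(p) + s).

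Example with p = 10%, s = 0.5, f = 50%: Φ(−1.28 + 0.5) = 21.7%, and 0.5 × 10% + 0.5 × 21.7% = 15.9%.

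| True share | Late share | s = 0.25 | s = 0.5 | s = 1.0 |
|---|---|---|---|---|
| 10% | 50% | 12.6% | 15.9% | 24.5% |
| 5% | 50% | 6.6% | 8.8% | 15.5% |
| 2.5% | 30-70% | 3.1-3.8% | 3.9-5.8% | 6.8-12.5% |

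A shift in the other direction would hide deficiency.

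**2. True link, equal timing.** Take 100 low-BMD and 100 high-BMD patients with true deficiency of 25% and 10%. The odds ratio is (0.25/0.75)/(0.10/0.90) = 3.0. With half the samples late in both groups:

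- s = 0.5: 34.0% versus 15.9%, odds ratio 2.7.
- s = 1.0: 43.9% versus 24.5%, odds ratio 2.4.

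The odds ratio is diluted. Power is not lost in this example (0.80 without a shift, 0.85 and 0.83 with it), because more patients fall below the cut-off.

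**3. No true link, unequal timing, by formula.** Take p = 10%, 100 per group, s = 0.5, with 30% late in one group and 70% in the other.

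- Group shares: a = 0.7 × 10% + 0.3 × 21.7% = 13.5%; b = 0.3 × 10% + 0.7 × 21.7% = 18.2%. The spurious odds ratio is 1.4.
- Difference d = 0.047; mean share 0.1585. Null SE = √(2 × 0.1585 × 0.8415/100) = 0.0517. Alternative SE = √[(0.135 × 0.865 + 0.182 × 0.818)/100] = 0.0515.
- Rejection rate = Φ[(0.047 − 1.96 × 0.0517)/0.0515] + Φ[(−0.047 − 1.96 × 0.0517)/0.0515] ≈ 15%.

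For s = 1.0 the shares are 18.7% and 30.2%, the odds ratio is 1.9 and the rate is 48%. With 40%/60% late the rates are 7% and 16%. With 50%/50% the rate stays at 5%.

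**4. No true link, by simulation.** There are 200 patients split at random into low and high BMD. The hormone value is standard normal, lowered by s if the sample is late. The outcome is the lowest quartile, tested by an uncorrected two-sided 5% chi-square test.

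| Late in low / high BMD | s = 0.25 | s = 0.5 | s = 1.0 |
|---|---|---|---|
| 45% / 45% | about 5% | about 5% | about 5% |
| 40% / 50% | about 6% | about 6% | about 8% |
| 30% / 60% | about 7-8% | about 13% | about 32% |
| 30% / 60%, Mantel-Haenszel by timing | about 5% | about 5% | about 5% |

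In the unadjusted 30%/60% case, about 87%, 98% and 100% of the significant results make the **high**-BMD group look deficient. That pattern would mask a low-hormone/low-BMD link. With the late shares exchanged, it would imitate one.

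**The case against.** The study calls itself mainly descriptive. The team saw the problem, asked for early samples, and may take all blood results from the records, so timing is probably recoverable. All of this stands and keeps the point modest. None of it is an analysis rule.

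The false-positive rates depend on a timing gap between BMD groups that the documents do not report. This also stands: without a gap the test keeps its level, and a gap of 40% versus 50% adds little. With a continuity correction, the 30%/60% rates fall to about 5%, 10% and 27%.

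Four stronger readings are tempting and not supported:

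- **That trauma effects will produce a false hormone-BMD link.** The protocol says only that values may be disturbed. Direction and size are not given, and unequal timing can hide a link as well as create one.
- **That SAP 1.a compares hormones with its control group.** Its first aim is limited to BMD and basic risk factors available in the controls, and hormones are not named. The hormone comparison with a standard population is in the protocol only.
- **That hormones are exempt from early sampling.** The footnote mark is on the whole blood-test row. Repeating the request on two laboratory lines need not release the others.
- **That restricting to pre-operative samples cures the problem.** Every sample is taken after the injury. The restriction removes the surgery effect, not the trauma effect, and may select patients by consent route or site.

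**Conclusion.** The point holds in a conditional form. The sampling window runs from before surgery to day 10, the protocol itself warns of disturbance, and SAP 1.a has no timing variable and names only a test that cannot adjust for one. Some parts of both documents were not available for review, so this means not addressed in the text that was.

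The description of deficiency and the protocol's standard-population comparison are open to bias whenever disturbance moves values in one direction. For the hormone-BMD hypothesis, the consequence depends on timing: a diluted odds ratio if it is equal across BMD groups, a created or masked link if it is not. In the simulated scenarios the unadjusted error rate runs from the nominal 5% to about 32%. The upper end needs both a 1 SD shift and a 30%/60% split, and neither is documented. The case for change rests on the protocol's own warning and the low cost of adjusting, not on any one of these rates.

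**What to change.** 1. Derive two variables from the records: time from trauma to blood draw, and whether the draw was before or after surgery. The protocol's Data section already covers blood results and accident information. That draw dates can be recovered with them is an assumption to confirm.
2. In SAP 1.a, report hormone results by sample timing.
3. For the hormone-BMD hypothesis, replace the unadjusted chi-square test with a Mantel-Haenszel analysis stratified by timing or a regression model, in either case including both timing variables.
4. For the protocol's comparison with a standard population, show all samples and, as a sensitivity analysis, early pre-operative samples only, with *early* defined in advance. State that this subset removes the surgery effect but not the trauma effect.

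**Cost.** Two derived variables, and a stratified or regression method in place of a simple chi-square test, which is more than a change of wording. The sensitivity subset will be smaller and possibly selected. Patients need no further procedure.

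### SAP 1.a relates BMD to hormonal status without separating women by menopausal status or hormone use, and omits the menstrual item that the protocol collects

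*Protocol*

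**What the plan says.** **Protocol, Recorded data.** The laboratory list has eight test lines and eight purposes. The seventh test line is "testosterone (men) / estradiol (women") and the seventh purpose is "hypogonadism". No gonadotrophin, estradiol cut-off or cycle-day rule is listed. Under Health indicators the protocol also records "Regular menstruation" and use of particular medication over the five years before the fracture. Hormonal drugs are not named there.

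**Protocol, Material and Method.** Eligibility is "Patients aged 18 to 59 years". Hormonal status is also to be compared with a standard population.

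**Protocol, Follow-up scheme.** Blood tests are marked pre-operatively and at day 1-10, with none at later visits. The footnote says: "Standard screening blood test shall be taken as early as possible, as they may be disturbed by trauma and surgery". In the laboratory list the early-sampling marker stands on the blood-count line and on "total calcium + albumin, parathyroid hormone (a.s.a.p. after trauma"), but not on the sex-hormone line.

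**SAP 1.a.** The title names hormonal status. The variable list includes sex, age, BMI, comorbidity, medication and "Laboratory tests including hormonal status", but no menstruation or menopause item. The second hypothesis reads: "Within the hip fracture group; different levels of BMD are associated with comorbidities, hormonal status and life style factors". For both aims the stated analysis is a Chi-square test on categorical data, with no stratification or adjustment.

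**The concern.** The age range takes in women who are cycling, women in the menopausal transition and women past it. As a matter of general physiology, estradiol can be low after menopause, during some hormonal treatments, in part of a normal cycle, and in pathological deficiency. One estradiol category does not say which of these applies.

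Menopause is also tied to age, and both bear on BMD. A crude test of BMD category against estradiol category in all women can therefore come out positive because postmenopausal women differ from premenopausal women, even if estradiol says nothing about BMD within either group.

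The stated purpose of 1.a is to find patients with an underlying cause for an early hip fracture. Expected menopause, hormone use, cycle phase and suspected pathology would lead to different readings of the same result. If they are merged, neither a reported prevalence of hypogonadism in women nor its association with BMD can be interpreted.

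**Working it through.** **1. No figure to reproduce.** The documents give no estradiol threshold, prevalence of low estradiol, sex split, menopausal share, alpha or power. The core of the point is therefore a comparison of texts.

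**2. Texts side by side**

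| Item | Protocol | SAP 1.a |
|---|---|---|
| Estradiol in women | listed, for hypogonadism | only as part of laboratory tests |
| Menstruation | collected | not listed |
| Menopausal status, cycle day | not listed | not listed |
| Medication | collected, hormonal drugs not named | listed, hormonal drugs not named |
| Age, sex | collected | listed |
| Estradiol categories | none given | none given |
| Stratification or adjustment | none given for this question | none given |

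SAP 1.b does carry a list of variables for adjustment. SAP 1.a has no counterpart, and the 1.b list omits menstruation too.

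**3. How mixing produces an association.** Let *a* and *b* be the shares with low BMD among postmenopausal and premenopausal women. Let *w* and *v* be the postmenopausal shares among women with low and not-low estradiol. Suppose estradiol carries no information on BMD within either group. The crude difference in low-BMD share is then

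[w·a + (1−w)·b] − [v·a + (1−v)·b] = (w − v)(a − b).

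It is zero only if w = v or a = b.

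**4. Illustration on assumed inputs (none is in the documents).** Take P = 50-70% of women postmenopausal, 90% of them low. Among premenopausal women take 15-25% hormone users, 50-80% of them low, and 10-20% of the rest low by cycle phase.

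- Premenopausal share low, q: from 0.15×0.5 + 0.85×0.1 = 0.16 to 0.25×0.8 + 0.75×0.2 = 0.35.
- w = 0.9P / [0.9P + (1−P)q]; v = 0.1P / [0.1P + (1−P)(1−q)].

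| P | q | w | v | w − v |
|---|---|---|---|---|
| 0.5 | 0.16 | 0.45/0.53 = 0.85 | 0.05/0.47 = 0.11 | 0.74 |
| 0.5 | 0.35 | 0.45/0.625 = 0.72 | 0.05/0.375 = 0.13 | 0.59 |
| 0.7 | 0.16 | 0.63/0.678 = 0.93 | 0.07/0.322 = 0.22 | 0.71 |
| 0.7 | 0.35 | 0.63/0.735 = 0.86 | 0.07/0.265 = 0.26 | 0.59 |

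At these four corners, 59-74% of any pre/post gap in low BMD would appear as an estradiol association.

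**5. How far this depends on the inputs.** A wider assumed grid takes M = 10-70% postmenopausal (all low), H = 0-30% hormone users among premenopausal women (all low), c = 0-30% low by cycle phase, and g = 2-40% true deficiency among premenopausal non-users. The share of low results due to menopause, hormone use or cycle phase is N/(N + D), with N = M + (1−M)H + (1−M)(1−H)(1−g)c and D = (1−M)(1−H)g.

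- Lowest: M = 0.1, H = c = 0, g = 0.4 gives 0.10/(0.10 + 0.36) = 22%.
- Highest: M = 0.7, H = c = 0.3, g = 0.02 gives 0.85174/(0.85174 + 0.0042) = 99.5%.
- The share exceeds one half at 137 of 144 grid points.

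**6. Premenopausal women only.** With true deficiency t, and every true case testing low, the true share of low results is t/[t + (1−t)q]. For t = 3% it is 0.03/0.3695 = 8% to 0.03/0.1852 = 16%. For t = 10% it is 0.10/0.415 = 24% to 0.10/0.244 = 41%. The result turns on t, which the documents do not give.

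**The case against.** The strongest reply is that the plan makes no wrong choice; it leaves a definition unstated. Neither document says that women will be classified by estradiol alone, and neither uses low estradiol as a category. This stands: a reader might infer such a rule, but the text only pairs a test with a purpose.

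Menopausal oestrogen loss is a legitimate exposure. The protocol's Background names hormonal deficiency as a risk factor and notes rising incidence in women around 50, and the 1.a hypothesis speaks of hormonal status, not pathology. This also stands. It is a reason to analyse menopause openly, not to merge it with suspected deficiency.

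SAP 1.a keeps age, sex and medication, so a rough separation is possible, and hormone use is not lost if the medication data cover it. Absence from a short SAP list does not remove menstruation from the dataset. Both points are fair. However, the list is not a bare abridgement of the protocol's, since it adds diet, anabolic steroids and relatives' fractures. Nor does any rule say how age, medication and estradiol will be combined.

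Two further inferences go too far. A single blood draw is not stated, since two early columns are marked and could mean either or both. Sampling is unconstrained only as to cycle day, because an early sample after trauma is requested.

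The study is mainly descriptive and this is one of many covariates, which limits the severity. It is nevertheless in the title and a hypothesis of 1.a.

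**Conclusion.** The point holds as a gap in the analysis plan. SAP 1.a, followed as written, would relate hormonal status to BMD across pre- and postmenopausal women with no stratification or adjustment, and without a menstrual item that the study already collects. The result would mix menopause and age with any pathological deficiency. Hormone users, and women sampled when estradiol is normally low, could be misclassified.

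The size cannot be computed from the documents. The percentages in the working rest wholly on assumed inputs and show the mechanism and its sensitivity, not an estimate. A reader might infer that low estradiol in this cohort will mostly be artefact. The documents do not support that: the share runs from 22% to 99.5% over the wider assumed grid, and its menopausal part is real oestrogen loss, not error. Weight: a cheap improvement.

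**What to change.** In SAP 1.a:

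- Add the menstruation item, and hormonal medication (contraception or hormone therapy, taken from the medication data), to the variable list.
- State how estradiol will be categorised.
- Analyse and report estradiol, and its association with BMD, separately by menopausal status, or by age band where that status is unknown. Keep current hormone users as their own category.
- Report menopause as an exposure in its own right.
- Do not label low estradiol alone as hypogonadism.

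If the interview does not already record age at menopause, it can be asked at an existing interview (in the ward, or at 4 months, 1 year or 2 years), including for women already enrolled.

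**Cost.** SAP wording and at most a short added question; no new blood test. The women among about 200 patients will fall into smaller subgroups, so cells will be sparse. Use few categories or exact tests. The headline prevalence of hypogonadism in women is likely to be lower.
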